Stress: Patients will not experience greater risks if randomized to one care approach over the other. The measures that will be conducted during the study include PROMIS instruments, surveys and brief functional tests (handgrip strength, ROM, LEGS functional measures). The risks to performing these patient reported outcomes and functional tests are very low. Although a minimal risk, completing surveys may cause stress to some participants who may believe that they are not providing correct answers to the study team. The survey questions have a very low psychological risk if participants are upset by questions that ask them to think about their own poor health or problems that are disturbing. Should a patient present, answer, or score in particular negative manner on the psychological measures we have implemented, a Distress Referral Protocol for the patient's safety. This protocol states that patients scoring one standard deviation above the normative range for this patient population will receive further evaluation by the clinical psychology service.

Physical Discomfort: Potential minor discomforts of some of the functional tests can include transient muscle soreness for all patients, whether in the study or not. Muscle soreness may occur when participants begin moving again after injury. This symptom is common following unaccustomed physical activity, and the duration of this soreness is generally up to 48 hours after the activity.⁵⁹ The study team members will explain this potential risk to all participants to minimize this stressor.

Protections Against Discomforts and Risks:

Consent and Confidentiality: Potential participants will be asked to read the informed consent form and to ask questions. The form will be written in simple, easy-to-understand language. We require the coordinator to review all key aspects of the study verbally. They will then question potential participants to ascertain whether they have understood the information. A copy of the signed and dated consent form will be given to participants, and the original document will be placed in subjects' individual study files, which will be stored in a locked, secure location in the OSMI (room 1135).

Stress: The study team will assure all patients that there are no "correct" answers on their survey responses. The Study Coordinator or Facilitators will be present at all times during data collection to help answer any questions that may be confusing. The survey questions have a small likelihood of low psychological risk if participants are upset by questions that ask them to think about their own poor health or problems that are disturbing. Participants are free to refuse to respond to any question that they believe may result in psychological disturbance.

Protection of Personal Health Information: Data will be used only in aggregate and no identifying characteristics of individuals will be published or presented. Confidentiality of data will be maintained by using research identification numbers that uniquely identify each individual. Safeguards will be established to ensure the security and privacy of participants' study records. Appropriate measures will be taken to prevent unauthorized use of study information. Data other than demographic information do not use names as an identifier. The research ID number will be used. The research records will be kept in a locked room in the OSMI. The files matching participants' names and demographic information with research ID numbers will be kept in a separate room and will be stored in a locked file that

uses a different key from that of all other files. Only the study team members will have access to these files, and they will be asked to sign a document that they agree to maintain the confidentiality of the information. After the study is completed, local data will be stored with other completed research studies in a secured storage vault within the OSMI.

Distress Referral Protocol: We acknowledge that for some patients, the level of psychological distress is beyond the capability of this program to provide the support necessary. In these cases, we will enact a Distress Referral Protocol. When a patient is identified as displaying evidence of elevated distress, a member of the care team will ask the patient to complete the BDI-II and STAI surveys, and then they will interview the patient about the evidence of distress. Patients, who have test scores greater than one standard deviation from the normal score, will be referred for further evaluation by the Psychology Service via the electronic medical record (EPIC) referral process.

The Psychology Service will consist of [name] assisted by graduate students, interns, and/or postdoctoral fellows in the Department of Clinical and Health Psychology at UF. Trainees on that service will be directly supervised by [name]. Those services will include a formal clinical interview, development of a diagnostic conceptualization, development of a treatment plan, and provision of treatment designed to reduce the patient's distress and improve coping. Treatment will usually consist of cognitive-behavioral interventions with strong scientific support for their efficacy. The BDI and STAI may be re-administered periodically to assess level of improvement after treatment has been initiated. Psychological treatment visits can be reduced in frequency or stopped following sufficient decrease in patient symptom scores and perceived distress.

Data Safety and Monitoring Plan.

A Data and Safety Monitoring Plan (DSMP) will be implemented to ensure the safety of all participants involved in the study and to ensure the validity and integrity of the data. The PI with the advice and assistance of the study team will monitor all aspects of safety. The Study Coordinator will meet monthly with the PI to review all Serious, Unexpected and On-site adverse events. Within 24 hours of initial confirmation, the PI will complete an Event notification and Evaluation form for all Serious, Unexpected and On-site adverse events which will be reviewed by the IRB. Non-serious event tracking will be monitored using the Health Events Questionnaire data collected following the running protocol. A summary of these non-serious events will be reported to the PI and IRB. A structured safety monitoring system will be established in order to both assure real-time participant care and unbiased monitoring of adverse outcomes. For ongoing participant safety, events will be assessed by the PI, physician, and Co-investigators to determine if they are Serious, Unexpected or On-site. If so, an event evaluation form will be completed that will include a description of the event, a classification of seriousness, assessment of potential relationship to the study, assessment of need for change in the consent or the study activities, a summary of known prior health issues, event outcome and a classification of the main organ system involved. The classification of potential relationship to the intervention is as follows.

Definite - Temporal pattern + Known or expected AE response pattern

Probable - Temporal pattern + Known or expected AE response pattern + Could not be explained by participant's clinical state

Possible - Temporal pattern + Known or expected AE response pattern + Could have been produced by a number of other factors

Unknown - Relationship for which no evaluation can be made.

Not related - AE for which sufficient information exists to indicate that the cause is unrelated to the study intervention

The study PI and Co-investigators will notify the IRB of any serious adverse events that result in death or additional medical care within 24 hrs. The PI, [name], can be reached at [contact].

8. Possible Benefits:

There is no direct benefit to any of the patients whose data are used in this study. However, there are indirect benefits of the analysis of these data. The study team completed research to determine what outcomes are important to patients who are receiving care after orthopedic surgery. Identification of common patient experiences and concerns helped to shape our research questions on the outcomes important to patients and caregivers. This is significant because we can effect meaningful change in how patients are managed during their hospital stay and beyond.

Analyze the risk-benefit ratio: This study poses relatively low risk to individuals. It poses a low risk of breach of PHI. The possibility of identifying processes that can improve patient care and safety is very helpful for patients, families and providers. These data can be used to help patients and providers in the future incorporate processes that can improve patient experience and outcomes after orthopedic trauma injury. The risk-benefit ratio is acceptable.

Conflict of Interest

The study team has no conflict of interest to report.

Sources of funding:

This project has received support from the Foundation for Physical Medicine & Rehabilitation, the National Athletic Trainers' Association and the W. Martin Smith Interdisciplinary Patient Quality and Safety Award.

References

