Randomization Process: The randomization process will be performed using a random number table and recorded separately into sealed envelopes. These envelopes will be randomly placed into patient folders. After the informed consent process, facilitator will open the randomization envelope. The patient will not know what group they have been randomized to, only the facilitator and study staff will know which group the patient is in. . .

Facilitators: The facilitators are an integral part of the study team. They have all of the proper training (IRB, HIPPA, NIH, etc.) to work with patients in health care and research settings. The Facilitators will be responsible for administering the surveys to collect the data on emotional well-being. The facilitators will also be familiarized with administering the *Transform-10* Program. The facilitators are supervised by the attending orthopaedic trauma physician ([name] or [name]), [name], and a clinical psychologist, [name]. [name], Drs. [name] and [name], and [name] will also serve as mentors for the facilitators as questions arise regarding the implementation of the *Transform-10* Program. The facilitators will make daily rounds with the trauma physician and other daily visits during the patients' hospital stay to ensure they are adhering to their treatment plan and to clarify any details about the patient's injury or treatment plan. The facilitators will serve as liaisons between the hospital staff, physician, clinic staff, and discharge planner. These individuals will be in daily communication with the study team, physician, and/or other hospital personnel to ensure patient safety and that the patients' medical questions are presented back to the attending physicians. Daily monitoring of facilitators by the attending orthopaedic trauma physician and study team will occur via morning conference prior to meeting with patients and a debriefing with the study coordinator at the conclusion of each day.

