Study Groups: The ICare will be compared to UsCare. This choice of comparators was made for several reasons. UsCare for orthopedic trauma involves surgical intervention, acute care therapies, post-acute rehabilitation and follow-up clinic visits after discharge. Psychosocial support and resources are commonly provided after discharge, but only if needed. ICare provides the simultaneous provision of psychosocial support and medical care beginning at admission to the trauma service. After hospital discharge Both study groups will be asked to come to the Human Dynamics Laboratory/Sports Performance Center at the Orthopaedic and Sports Medicine Institute (this building is where they will have follow up visits with their physician) about an hour early to complete the functional assessments and questionnaires. For the ICare group, the remaining steps for the *Transform-10* Program will be reviewed within this time. After the assessments and questionnaires, the participant will be escorted to the clinics on the second floor to see the physician.

1. Usual Care (UsCare). Post-operative care is based on widely-accepted recommendations⁸ and on the current understanding of injury treatment. The key components of the care system include medical stabilization, injury repair, discharge planning and physical rehabilitation. Usual Care includes radiographic imaging and administration of pain medication and antibiotics, skin care and range of motion of the injured area. The attending physician visits with the patient a minimum of once per day and the nursing staff attends to patient care approximately once every four hours. Upon admission to acute care, the attending physician (*[name] or [name]*) will introduce the team to the patient and explain the purpose and activities involved in the medical approach. The patient will have the ability to ask questions and express concerns. Each patient will be assigned a Facilitator who will have contact with the patient. All medical processes will proceed under the guidelines of Usual Care. The Facilitator will visit the patient when the Attending Physician performs rounds only. If applicable, the Clinical Psychologist (*[name]/ Postdoctoral Fellow*) will review patient concerns and issues as presented to him by the Attending Physician. The initial measures will be obtained in the hospital setting, and follow-up measures will be collected in the typical outpatient times out Protocol

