4. Set goals for recovery	Contemplate the question, " What gives my life meaning? " Break up the rehabilitation process into small increments to make the recovery process manageable, measurable and controllable.
5. Take ownership of your journey	Seize responsibility and take charge of your recovery to achieve goals. This provides daily purpose and increases self-efficacy. Develop resilience. Draw a 'care map' for you and your recovery. Adhere to safety plans from your doctor.
6. Establish lifelines with others	Use the "buddy system". Rely on a non-family member to be an objective soundboard to help deal with possible physical and psychological setbacks.
7. Mobilize all resources	Mobilize and access free resources. Sunlight, fresh air and free outdoor activities (stage-appropriate exercise) are essential to helping the body and mind recover from trauma.
8. Rally your social support	Bring family and friends together to assist in recovery.
9. Take steps to return to normal	Keep life activity patterns (sleep, diet, exercise) and body rhythms as close to normal as possible.
10. Reduce available stressors	Replace avoidable stressors with positive thoughts and activities such as mindfulness, relaxation and imagery reduces flashbacks and stress.

Data collection and Measurements: The study team will follow a systematic process for data collection. Each patient will have a folder of electronic case report forms on the REDCap repository. Form design will follow *Good Clinical Practice* rules. Within each patient folder, there will be a study checklist. When electronic case report forms are completed, REDCap updates the status to indicate 'completion'. Data will be validated at the time of input by computerized controls that ensure the validity and quality. REDCap contains system integrity measures to guarantee the integrity of the system and to protect against data loss. On a weekly basis, all records will be reviewed by the Facilitators and the Clinical Coordinator.

Patient-Reported Outcomes. Patient-reported outcomes will be primary measures of the study. Patients are the most important source of information regarding the outcomes of interest, because this study focuses on patient perceptions of functional QOL and emotional well-being. At study entry, all patients will be asked to complete surveys with a Facilitator. The combination of proposed subjective and additional objective measures will create a complete picture of the patient experience.

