Sample Size: A sample size of 100 was determined in an *a priori* manner using G*Power software program.^{55,56} Anticipating that the study population will be younger but otherwise similarly distributed as that of Zimmerman et al.⁴² the sample size, N=100, was determined to be sufficient to have a medium effect size (Cohen's $d=0.60$, power of 0.80, and alpha of 0.05). This then translates into variable detectable mean differences depending on the outcome. For example, a 6.4 point difference in the State Trait Anxiety Index (STAI; one of the psychological measures for the study) can be detected assuming a standard deviation (SD) of 10.0; for AROM a 8.3 difference with an 12.0 SD. Linear mixed effects models will be used to analyze differences between UsCare and ICare in continuous outcomes.⁵⁷ Fixed effects will include randomized treatment group, time of measurement, baseline measurement, and covariates. An interaction term between treatment group and time will be modeled to assess how longitudinal changes in the outcomes differ between treatment groups. Subject-specific effects (random effect) will also be modelled to account for intra-individual correlation across measurement occasion. For categorical outcomes, a similar approach will be employed using generalized linear mixed models with a logit-link function (i.e. mixed-effects logistic regression). Sensitivity analyses will compare the impact of different covariance structures underlying the repeated measurements (e.g. unstructured, autoregressive,⁵⁸ and compound symmetry) on the results from the mixed-effects models.

7. Possible Discomforts and Risks:

Consent: Written informed consent will be obtained after explanation to participants about all procedures and time commitments. The team members will explain to prospective participants the purpose, methods and extent of the study. Potential participants will be asked to read the informed consent form and to ask questions.

Confidentiality: There is the potential minor risk of breach of confidentiality of information

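### The envelope procedure describes no audit trail for allocation, and the text does not place the baseline measures before the facilitator learns the arm

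*Protocol*

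**What the plan says.** All of the relevant text is in section 6 of the protocol. The SAP does not cover randomisation or the timing of baseline.

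- **Sequence.** Randomization Process: "The randomization process will be performed using a random number table and recorded separately into sealed envelopes".
- **Assignment to patients.** The next sentence adds a second step: "These envelopes will be randomly placed into patient folders".
- **Opening.** "After the informed consent process, facilitator will open the randomization envelope".
- **Who knows the arm.** The patient is not told; "only the facilitator and study staff will know which group the patient is in".
- **Who collects the data.** Facilitators: "The Facilitators will be responsible for administering the surveys to collect the data on emotional well-being". Patient-Reported Outcomes: "At study entry, all patients will be asked to complete surveys with a Facilitator".
- **Who delivers the intervention.** The Integrated Care paragraph gives Transform-10 to the same group of facilitators, starting on the trauma floor.
- **When baseline is taken.** The Usual Care paragraph says "The initial measures will be obtained in the hospital setting". Statistical Analysis calls the first time point admission. Neither refers to the envelope.
- **How baseline is used.** Sample Size: "Fixed effects will include randomized treatment group, time of measurement, baseline measurement, and covariates". Statistical Analysis also includes admission among the time points of the treatment-by-time model.

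**The concern.** There are two separate questions.

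The first is whether the allocation a patient received can be traced to the one generated for that patient. Once sealed envelopes have been shuffled into folders, the order of the random number table no longer corresponds to the order of enrolment. Something else has to carry the link: a number on the envelope, a study ID, or a log of which envelope was opened for whom and when. The protocol describes none of these. If a folder were exchanged before use, or set aside and another taken, the described records would look the same as if nothing had happened.

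The second is whether baseline is recorded before anyone handling the patient knows the arm. Facilitators open the envelope, sit with patients for the surveys and deliver the programme. If opening comes first, facilitator expectation or early Integrated Care contact could move the baseline in one arm. The primary outcomes are patient-reported, and the model adjusts for baseline, so such a shift would carry into the treatment estimate.

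**Working it through.** The plan states no figure on this point, so the check sets the text side by side. The one piece of algebra shows how a shifted baseline would act.

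**Step 1. Does the folder shuffle damage randomness?** No. A random permutation of a random sequence is still random. What is lost is the correspondence between list and enrolment order.

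**Step 2. What would restore that correspondence?**

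| Control | In the described procedure? |
|---|---|
| Sealed envelopes | Yes |
| Opening only after consent | Yes |
| Opaque envelopes | Not stated |
| Sequential numbers, used in enrolment order | Not stated |
| Link from envelope to study ID | Not stated |
| Holder of the list outside recruitment and delivery | Not stated |
| Dated log of openings | Not stated |

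The nearest candidate for a check is the weekly record review under Data collection and Measurements. It is carried out by the facilitators themselves with the Clinical Coordinator, and allocation is not mentioned.

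**Step 3. Is the order of baseline and opening fixed?** Three places bear on baseline timing: study entry (Patient-Reported Outcomes), in hospital (Usual Care) and admission (Statistical Analysis). One place bears on opening: after consent (Randomization Process). Two orders fit all four statements:

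- consent, baseline measures, envelope;
- consent, envelope, baseline measures.

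The text does not choose between them. Research Design says Figure 1 gives the study flow. That figure was not readable in the copy reviewed and may show the order.

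**Step 4. What would follow under the second order?** Let A be 1 for Integrated Care and 0 for Usual Care, and let B be the baseline free of arm influence. Ignoring residual error, suppose follow-up is

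Y = a + τA + βB,

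and the recorded baseline is B* = B + δA, where δ is the shift caused by the arm being known or begun. Substituting B = B* − δA gives

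Y = a + (τ − βδ)A + βB*.

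The baseline-adjusted difference is therefore off by −βδ. In the contrast of follow-up with admission, which the treatment-by-time term uses, the arm difference in recorded change is off by −δ. If δ = 0, both errors vanish. The documents give neither β nor δ, nor the sign of δ, so no size or direction can be stated.

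**The case against.** The case for the plan is substantial.

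- **Concealment is partly planned.** Envelopes are sealed, placed in folders beforehand and opened only after consent. This stands.
- **A list may exist.** The sentence on recording the randomisation separately is ambiguous and could mean that a list is kept. This stands as far as it goes: silence about a log does not show that there is none.
- **The order may be in Figure 1.** A flow diagram is where consent, baseline and randomisation would normally be set out. This stands, and makes the baseline part conditional.
- **Patients are meant to be blind.** A facilitator's knowledge is a weaker route to bias when the answers come from a patient who does not know the arm. This lowers the likely δ. It does not remove the route, because a facilitator sits with the patient and the intervention itself could begin before baseline is recorded.

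A reader might infer several stronger things that the text does not support. One is that allocation cannot be audited at all; the documents show only that no audit trail is described. Another is that the envelope is opened immediately after consent; the wording allows steps in between. A third is that baseline is taken with the arm known; the order is unstated. A fourth is that the lack of blocks or strata biases the comparison. Chance imbalance is not bias, and stratifying by injured limb would leave no clear place for the multiply injured patients whom the trial admits.

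**Conclusion.** The point holds in a limited form. As described, the allocation procedure has no numbering, study-ID link or log that would reveal a swapped or re-picked folder, and the people who open the envelopes also collect the surveys and deliver the intervention. This part rests on the Randomization Process and Facilitators paragraphs, and assumes that no undocumented log or numbering is in use.

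The second part is conditional. Unless Figure 1 shows baseline before opening, the plan leaves room for a baseline recorded after the arm is known, and the mixed model would carry any resulting shift into its estimates.

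Nothing here shows that allocation was subverted or that baseline was contaminated, and the documents do not allow the size of either effect to be derived. This is an inexpensive improvement worth making, not a finding that the randomised comparison is invalid.

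**What to change.** 1. Replace the folder step with a pre-generated allocation list released through REDCap, which the study already uses. Alternatively, use sequentially numbered, opaque, sealed envelopes tied to study ID and opened in enrolment order.
2. Have the list or envelopes prepared by an existing team member who neither recruits nor acts as a facilitator.
3. Keep a dated log of each release: study ID, envelope or list number, and the person who opened it.
4. State in the protocol that allocation is released only after consent and after the baseline surveys and handgrip measure are completed and saved. Check that Figure 1 agrees.
5. For patients already randomised, document any surviving list and the actual order of baseline and opening.

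The cost is a short amendment and some set-up, with no extra staff. The limitation is that patients already randomised stay under the old scheme. For them, step 5 can record what happened but cannot change it.
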